## **Method**

### **Experimental Design**

A three-group by two-assessment mixed prospective design will be used in this study. Participants will be randomly assigned to the order of each group and condition. See *Figure 1* for flowchart of the proposed study.

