### **Participants**

G\*Power 3, a power analysis program, developed by Faul, Erdfelder, Lang, and Buchner (2007), was used to determine sample size. In order to achieve a power of  $\phi = .80$  with two measurements and three groups at a medium effect size of .25, the analysis suggests a total sample size of at least 36 participants. Inclusion for participation will include fluency in the English language, being 18 years of age or older, own or have access to a mobile phone, and report discomfort with dental related care. The participants will receive a compensation of \$40.00 upon completion of the study. This study will adhere to the guidelines presented by the

American Psychological Association for treatment of human research participants. In order to participate, subjects will be required to sign an informed consent statement that will be approved by the West Virginia University Institutional Review Board.

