Participants in the treatment group will receive daily text messages as a reminder to conduct the exposure. Participants will be asked to follow the link and sign in each day with their mobile phones. Before each exposure video, the participants will rate expected distress on the SUDS. Then the participants will be asked to watch a video depicting dental care-related phobic material. After viewing the exposure video, participants will rate actual distress experienced on the SUDS. The participants will then be prompted to watch the video again. If the participant decides to view the video again, they will go through the same procedure of pre-rating fear and anxiety, watching the video, and post-rating fear and anxiety. Finally, the participants will be prompted to complete the procedure once more. After completing the procedure three times, the participants will no longer be prompted, however, they have the ability to complete the procedure two more times if they so desire.

The participants in the treatment group will be randomly assigned by previously prepared sealed opaque envelopes to video content (i.e., first- or third-person perspective). After 1-week of first or third video perspective, the participants will be assessed by the researcher via

telephone. Questions on the PQ and the DFS will be answered by the participants. After the assessment, participants in the first-person perspective will be informed that the video content will change to third-person perspective. Participants in the third-person condition will be informed that the video content will change to first-person perspective. At the end of the two weeks, participants will be asked to return in person for a follow-up and to receive \$40.00 compensation. The follow-up assessment will consist of the DBAT, completing the DFS, answering the PQ, and rating acceptability of using a mobile phone as a mean of self-directed exposure.

The control group will be assessed on the DFS after one week via telephone. After the two weeks the participants in the control group will be asked to return for a follow-up assessment and receive \$40.00 compensation. The assessment will consist of the same as the treatment group. At the follow-up session, participants in the control group will be offered the same treatment, for ethical reasons, as the experimental group, however, the data will not be analyzed.

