Proposed Analyses

Rates of procedure adherence (i.e., watching the video at least three times daily) will be assessed in order to examine the study's first question. The second question will be assessed by examining participants' rating of acceptability on the AARP with using a mobile phone as a method for self-directed exposure.

There will be 3 (group) x 2 (assessment) mixed measures analyses of variance (ANOVAs) which will be conducted to assess the first hypothesis regarding treatment effectiveness, with the DFS, and various DBAT measures (i.e., avoidance/escape, cardiac response, and SUDS verbal reports) as dependent variables. Sensitivity analyses will be conducted for baseline measurements. In order to examine the second hypothesis, a paired sample *t*-test assessing the relation of video perspective and scores on the PQ will be conducted.

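### The week-1 DFS is collected in every group but has no stated analysis; a three-occasion mixed model would use it and keep people without a week-2 score, for a modest gain

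*Protocol*

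**What the plan says.** The Protocol (Procedure) has the DFS administered three times: at the first visit, by telephone at week 1, and in person at week 2. For the treated participants the week-1 call is described as "Questions on the PQ and the DFS will be answered by the participants"; for the waitlist, "The control group will be assessed on the DFS after one week via telephone". Straight after that call the videos are swapped: "participants in the first-person perspective will be informed that the video content will change to third-person perspective", and the other treated group changes the opposite way. The DBAT is done only at the first and last visits.

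The design and analysis have two occasions. Protocol, Experimental Design: "A three-group by two-assessment mixed prospective design will be used in this study". Protocol, Participants: the power calculation was made "with two measurements and three groups at a medium effect size of .25", and "the analysis suggests a total sample size of at least 36 participants". SAP: "There will be 3 (group) x 2 (assessment) mixed measures analyses of variance (ANOVAs", with the DFS and the DBAT measures as outcomes.

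The SAP does not name the two assessments and gives no rule for missing scores. The one sensitivity analysis it mentions concerns baseline.

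**The concern.** One of the three DFS scores collected from every participant has no stated use. The DFS shares its ANOVA with the DBAT, which does not exist at week 1, so baseline and week 2 is the only pair that fits every listed outcome.

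Two things follow from that reading.

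- A conventional two-occasion mixed ANOVA needs both scores. Someone lost after the week-1 call would be excluded despite having two DFS values. That costs power in a small trial. It can also bias the comparison if leaving depends on how fearful the person still was at week 1.
- By week 2 both treated groups have seen both videos and differ only in order, including which was seen last. Week 1 is the only DFS occasion at which the groups have seen first-person only, third-person only, or nothing. If that contrast is not written down beforehand, any later use of it is post hoc.

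**Working it through.** **Inputs.** From the Protocol (Participants): f = .25, three groups, two measurements, N = 36, power .80. From the Protocol (Self-Report Measures): DFS test-retest correlation .88, used as the top of the correlation range. Assumed because not stated: alpha .05, 12 per group, the correlations between occasions, and dropout of 0–30% at week 2, with every dropout having given a week-1 score.

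**1. The plan's own figure.** Noncentral F with λ = f²·N·m/(1 − r) and denominator df (N − 3)(m − 1). At r = .5 and N = 36, λ = .0625 × 36 × 2/.5 = 9.0.

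- Main effect of time: power .829, and 36 is the smallest multiple of 3 reaching .80. The stated figure reproduces.
- Group-by-assessment interaction, which tests Hypothesis 1: power .729. It needs N = 42, or r of about .58 or more for 36 to suffice.

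**2. Completers-only ANOVA.** At r = .5, interaction power is .729 with 36 people, .685 with 33 and .635 with 30. At r = .7 it is .92 with 36 and .86 with 30.

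**3. Using all three occasions.** The interaction tests change from baseline to week 2, so what matters is how well baseline and week 1 predict that change. Write r01, r02, r12 for the correlations baseline–week 1, baseline–week 2 and week 1–week 2, with unit variances.

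- R²(week 2) = (r02² + r12² − 2·r01·r02·r12)/(1 − r01²)
- R²(change) = 1 − [1 − R²(week 2)]/[2(1 − r02)]
- Effective n = 1/[(1 − R²)/30 + R²/36], with R² for the change and 30 of 36 completing

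| r01 / r02 / r12 | R² (change) | Effective n | Share of the 6 recovered |
|---|---|---|---|
| .88 / .88 / .88 | .266 | 31.4 | 23% |
| .5 / .5 / .5 | .333 | 31.8 | 29% |
| .7 / .7 / .8 | .464 | 32.5 | 42% |
| .7 / .6 / .8 | .554 | 33.1 | 51% |

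For the third row: R²(week 2) = (.49 + .64 − .784)/.51 = .678; R²(change) = 1 − .322/.6 = .464; effective n = 1/(.536/30 + .464/36) = 32.5.

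**4. Efficiency and power at r = .5 throughout.**

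| Week-2 dropout | Relative efficiency | Power, completers only | Power, three-occasion model |
|---|---|---|---|
| 0% | 1.00 | .729 | .729 |
| 10% | 1.03 | .675 | .691 |
| 20% | 1.07 | .614 | .646 |
| 30% | 1.11 | .545 | .592 |

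The gains are 1.6, 3.2 and 4.7 points at 10, 20 and 30% dropout. With all correlations .88, relative efficiency is 1.03, 1.06 and 1.09, and power is at least .99 either way.

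Not all of the gain comes from week 1, since the model also keeps the dropouts' baseline scores. At r = .5 and 20% dropout, the variance of a group's mean change falls from .1042 (completers) to .0990 (adding baseline only) to .0972 (adding week 1). At .88 the sequence is .0250, .0247, .0237, so there most of the gain is from week 1.

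**5. Bias.** If treated participants leave according to week-1 DFS, and Δ is the resulting shift in completers' mean week-1 score in SD units, the completers' mean change is biased by (r12 − r01)·Δ. With equal correlations this is zero. With r12 = .8 and r01 = .7, the multiplier is .1. A large-sample simulation with a true effect of −.80 SD, and the log-odds of leaving rising by 1 per SD of week-1 DFS, gave completers-only estimates of about −.81, −.82 and −.825 at 10, 20 and 30% treated dropout. That is an overstatement of about 1–3%. The likelihood estimate stayed at −.80.

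**The case against.** The strongest reply is that the harm is small and conditional. With complete data, week 1 adds nothing to the week-2 contrast. The study lasts two weeks and pays on completion, so dropout may be low. Even the 3% bias is about .024 SD, against a standard error for 24 versus 12 of √[2(1 − r)(1/24 + 1/12)] = .35 SD at r = .5 and .27 at r = .7, so under a tenth of a standard error. Where recovery is proportionally larger (baseline–week 2 correlation near .7), power is already .92 with 36 people. All of this stands, and it sets the size of the point.

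Three stronger readings are tempting, and the documents do not support them.

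- A reader might infer that the SAP says week-1 DFS is discarded and people without week 2 are excluded. It says neither. These are the natural reading and the default behaviour of the method.
- A reader might infer that the plan omits the test of a study hypothesis. Hypothesis 1 compares exposure with control, and Hypothesis 2 is about perspective and presence, not fear. With 12 versus 12 and a difference of .5 SD, the week-1 contrast would have power of only about .27–.37 even with baseline adjustment.
- A reader might infer that the treated groups are interchangeable at week 2. They still differ in video order and in the most recent perspective; only cumulative exposure to the two videos is the same.

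It can also be said that naming the two assessments and stating a missing-data rule would close the gap. That would be the minimum. The mixed model does both and uses scores already collected.

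**Conclusion.** The point holds as a modest improvement in method. The DFS is measured three times in every group, and the only planned analysis has room for two. On the natural reading, week 1 goes unused and people without a week-2 score drop out of the analysis.

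The gain is nil with complete data. At an assumed 30 of 36 completers, effective n is about 31.4–33.1 instead of 30, which recovers 23–51% of the loss for the correlations tried. At r = .5 and 10–30% dropout it is about 2–5 power points. The bias removed is 0–3%, and only if leaving depends on week-1 DFS and week 1 correlates more closely with week 2 than with baseline. Dropout, correlations, alpha and allocation are all assumptions. The figures do not support a claim of serious information loss or of material bias.

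**What to change.** For the DFS, replace the two-assessment ANOVA with a linear mixed model on all randomised participants:

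- Outcomes at baseline, week 1 and week 2; categorical time, group and group-by-time; unstructured covariance; a small-sample degrees-of-freedom method such as Kenward–Roger, which matters with about 36 people.
- Hypothesis 1 test: change from baseline to week 2, exposure versus waitlist. Do not substitute an average of weeks 1 and 2. Its higher efficiency (1.33 with complete data) assumes the same effect at both weeks, and it would lose power if the effect is still growing.
- First- versus third-person at week 1: report as exploratory, with an interval.
- State which two assessments the DBAT analyses use, and how missing scores are handled.

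The cost is SAP wording and slightly more analysis work, with no new data. Week 1 is by telephone, but that mode is common to all groups, and categorical time absorbs a common shift.

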Proposed Analyses

Rates of procedure adherence (i.e., watching the video at least three times daily) will be assessed in order to examine the study's first question. The second question will be assessed by examining participants' rating of acceptability on the AARP with using a mobile phone as a method for self-directed exposure.

There will be 3 (group) x 2 (assessment) mixed measures analyses of variance (ANOVAs) which will be conducted to assess the first hypothesis regarding treatment effectiveness, with the DFS, and various DBAT measures (i.e., avoidance/escape, cardiac response, and SUDS verbal reports) as dependent variables. Sensitivity analyses will be conducted for baseline measurements. In order to examine the second hypothesis, a paired sample *t*-test assessing the relation of video perspective and scores on the PQ will be conducted.

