## **Study Protocol**

The proposed study will examine the question of whether phobic individuals will use a mobile phone in self-directed exposure therapy. A second question is whether phobic participants will find the use of a mobile phone as an acceptable means of conducting self-directed exposure therapy.

Accompanying these two research questions are additional specific hypotheses. The first hypothesis is that filmed exposure stimuli, available on a mobile phone, will be associated with greater fear reduction in a self-directed exposure group relative to a control group. The second hypothesis is that greater presence will be reported with first-person perspective versus third-person perspective.

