### **Procedure**

The participants in the study will be recruited through advertisements in local newspapers, posted flyers on the campus of West Virginia University, and advertised on Craigslist (e.g., a website that provides services/goods). Upon arrival to the study, participants will be given a written informed consent form and information on study procedures. The researchers will discuss the process of the study and what is expected of the participant. The participants will be informed that they will receive \$40.00 for compensation at the completion of the study. After agreement to enlist in the study and completion of the ADIS-5, the participants will be randomly assigned to group (i.e., 2-week waitlist or treatment group) by previously prepared sealed opaque envelopes, complete the demographic questionnaire, conducted the DBAT, and answer the DFS. The researchers will then provide a 15-minute demonstration on how to conduct self-directed exposure therapy on the participant's mobile phone, and how to rate

SUDS. The researchers will describe that watching the exposure video three times per day is the ideal, one time per day is the suggested minimum, and viewing the exposure video five times per day is the suggested maximum.

The video will display a typical preventive visit to the dentist, including walking into the dental office, being called back for treatment by the dental assistant, sitting in the dentist chair, and seeing the dentist perform a teeth cleaning. The video will be 15-minutes in length, and be recorded by the researchers in both first- and third-person perspective. The actors in the video will be confederates and have knowledge about the purpose of the video. The actors in the video are from the School of Dentistry at West Virginia University.

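### Hypothesis 1 compares exposure with waitlist, but the SAP tests it with a three-group ANOVA and names no contrast, so the planned 2-df interaction does not answer it

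*SAP*

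**What the plan says.** The opening section of the protocol (Study Protocol) states Hypothesis 1 as "greater fear reduction in a self-directed exposure group relative to a control group". Under Procedure, participants are first "randomly assigned to group (i.e., 2-week waitlist or treatment group) by previously prepared sealed opaque envelopes". Those in the treatment arm are then randomised to start with the first- or third-person video, and they switch after one week: "participants in the first-person perspective will be informed that the video content will change to third-person perspective", and "Participants in the third-person condition will be informed that the video content will change to first-person perspective". By the two-week visit both treated subgroups have therefore been assigned both videos and differ only in sequence.

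For the analysis, the SAP (Proposed Analyses) says: "There will be 3 (group) x 2 (assessment) mixed measures analyses of variance (ANOVAs) which will be conducted to assess the first hypothesis". The outcomes are the DFS and the DBAT measures (avoidance/escape, cardiac response, SUDS). The SAP does not say which ANOVA effect decides the hypothesis. It names no contrast, no pooling of the two orders and no follow-up test. One sentence promises sensitivity analyses for baseline measurements, without saying that the main test adjusts for them.

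**The concern.** The question has two sides and the test has three groups. Group by assessment is the effect that addresses differential fear reduction. With three groups it asks whether any of them changed differently from the others. Two things follow.

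- **A significant result does not identify its source.** It may reflect exposure against waitlist, one order against the other, or both. No hypothesis concerns order, and perspective has its own paired t-test on presence scores. Because the SAP names no next step, the comparison that decides Hypothesis 1 would be chosen after the data are seen.
- **A null result may miss a real benefit.** If both orders work about equally, all the signal lies on one contrast, and the second degree of freedom only dilutes the test.

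Separately, with two assessments the interaction is a test on change scores. That is valid under randomisation but less efficient than adjusting for baseline.

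**Working it through.** **Inputs from the protocol (Participants):** f = .25, three groups, two measurements, target power .80, N = 36. **Assumed, because not stated:** alpha .05; 12 per group (18/9/9 also shown); correlation rho between the two assessments of .3, .5 or .7, and also .88, the DFS test-retest value, which is the only figure of this kind in the documents. No dropout is applied. SD means the SD of the outcome at one assessment, taken as equal at both.

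**The plan's own figure.** For a repeated-measures test, lambda = f²·N·2/(1 − rho), with N − 3 error df. At rho = .5 and N = 36, lambda = .0625 × 36 × 2/.5 = 9.
- A 1-df test needs N = 34, or 36 in equal groups, where power is .829. This reproduces the protocol's 36.
- The 2-df interaction needs N = 42; its power at 36 is .729. It gives 36 only with other unstated inputs, such as rho = .6. The protocol does not say which test was sized.

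**Effect implied by f = .25.** If each order beats waitlist by d in change, (2/9)d² = 4f² = .25, so d² = 1.125 and d = 1.06 SD.

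**Power when the orders work equally.** All of lambda falls on the contrast. Baseline adjustment changes the residual variance from 2(1 − rho) to 1 − rho², which multiplies lambda by 2/(1 + rho), and uses one more error df.

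| rho | lambda | 2-df interaction | contrast only | adjustment only (2 df) | adjusted contrast |
|---|---|---|---|---|---|
| .3 | 6.43 | .57 | .69 | .77 | .86 |
| .5 | 9.00 | .73 | .83 | .85 | .92 |
| .7 | 15.00 | .92 | .96 | .96 | .98 |
| .88 | 37.50 | >.999 | >.999 | >.999 | >.999 |

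Simulation (20,000 runs) gives slightly lower adjusted-contrast figures: .853, .910 and .980 at .3, .5 and .7. With 18/9/9, the same d and rho = .5, the interaction has .78, the contrast .87 and the adjusted contrast .945 (simulated .936).

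**Significance when average exposure equals waitlist.** Set the changes relative to waitlist at +d/2 and −d/2, that is ±0.53 SD. Then lambda = 12 × 2 × (d/2)²/[2(1 − rho)] = 3.375/(1 − rho) = 4.82, 6.75 and 11.25 at .3, .5 and .7. The interaction is significant with probability .45, .60 and .83; the contrast stays at .05. With 18/9/9 the interaction figures are .35, .47 and .70. At half that separation (±0.27 SD, 12 per group) the interaction gives .18 at rho = .5 and .61 at rho = .88.

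**Power when the orders differ.** With rho = .5, the better order held at d and the other at kd:

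| k | 2-df interaction | contrast | adjusted contrast |
|---|---|---|---|
| .75 | .63 | .72 | .84 |
| .5 | .60 | .59 | .71 |
| 0 | .73 | .31 | .39 |

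For rho from .3 to .7, the unadjusted contrast falls behind the interaction when k is below .49 to .54, and the adjusted contrast when k is below .26 to .43.

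**The case against.** - **The group structure is inferred.** No section lists the three groups, the flowchart is not available in the text, and the SAP never uses the word interaction. This is true. But waitlist plus two orders is the natural reading of Procedure, and the mismatch between one comparison and a three-group test is in the text itself.
- **The case where average exposure equals waitlist is strained.** It needs one sequence to do worse than waitlist, although both sequences contain the same videos. This stands as a comment on likelihood. The probabilities illustrate the problem and are not forecasts, and they shrink with a smaller order difference or with 18/9/9 allocation. The logical point does not depend on them.
- **The power gain from the contrast is modest and conditional.** It is about .12, .10 and .04 at correlations .3, .5 and .7, and nothing material at .88. If only one order works, the contrast is clearly worse (.31 against .73 at .5). Both statements are correct and limit the power argument.
- **Baseline adjustment is a separate matter of efficiency.** This is fair, and it is why its contribution is shown separately. The contrast is worth specifying without it.
- **Assignment is listed before the baseline DBAT and DFS.** If participants already know their group, the baseline could be affected. That would harm the planned change-score ANOVA as well, so it is no reason to prefer the current test.
- **Several outcomes remain.** A contrast for each outcome does not settle which outcome decides the hypothesis. That is a separate question.

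**Conclusion.** The concern holds. Followed as written, the SAP does not by itself answer Hypothesis 1, whatever alpha, correlation or allocation applies. The power cost depends on assumptions: at N = 36, f = .25 and a correlation of .5, the 2-df interaction has .73 where the contrast has .83 and the adjusted contrast .92, provided that the orders work about equally. That is the reasonable planning case, since both orders are assigned the same two videos. At a correlation of .88 only the interpretation problem remains. The planned ANOVA is a valid test, but of a broader question than the one asked. This should be changed, and the change is cheap. Confidence is medium, because the groups are inferred and the correlation is not stated.

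**What to change.** For each outcome, test Hypothesis 1 with an ANCOVA of the two-week score on its baseline score, using one pre-specified contrast: the mean of the two video orders minus waitlist (weights ½, ½, −1). State that this contrast decides the hypothesis for that outcome, and report the difference between orders as secondary. At a minimum, pre-specify the same contrast on change within the planned ANOVA.

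The cost is SAP wording only; no new data are needed. At baseline, participants "conducted the DBAT, and answer the DFS". At two weeks, for the treatment group, "The follow-up assessment will consist of the DBAT, completing the DFS", and for controls, "The assessment will consist of the same as the treatment group". The price is lower power than the interaction if one order does much less than the other, below the break-even points given above.

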#### **Abbreviated acceptability rating profile (AARP; Tarnowski & Simonian, 1992).**

The AARP consists of 8-items that assess acceptability of treatment. Refer to appendix E. Items are rated on a 6-point Likert-type scale ranging from 1 (*strongly disagree*) to 6 (*strongly agree*). Good psychometrics have been demonstrated with the AARP (Cronbach's alpha ranging from .93 to .97; Caporino & Karver, 2012; Tarnowski & Simonian, 1992). The AARP was slightly modified to fit the current study.

**Dental Behavior Avoidance Test (DBAT).** In a laboratory furnished to exemplify a dental operatory, the DBAT will be conducted, consistent with prior research by McNeil, McGlynn, Cassisi, and Vrana (1989). The DBAT will consist of eight steps that simulate a dental examination, and each step will last up to 60 seconds. Escape from, or avoidance of, each step will be allowed, and will constitute a measure of escape/avoidance (i.e., total number of seconds of escape/avoidance behavior). A researcher will portray the dentist, and an undergraduate research assistant will portray the dental assistant. A maximum-distress SUDS rating will be reported by the participants at the end of each step of the DBAT. Throughout the procedure, participants' heart rate will be measured using a computer that controls a Coulbourn Instrument to measure ECG data. A four minute baseline will be recorded prior to the start of the DBAT. Before initiating the next step in the procedure, there will be a 60 second baseline recording.

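### Hypothesis 1 is tested on four co-equal outcomes with no primary outcome, alpha, multiplicity control or success rule, so its false-positive rate is not controlled and mixed results have no pre-set reading

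*SAP*

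**What the plan says.** The Protocol's opening section (Study Protocol) states Hypothesis 1 with a direction: the filmed stimuli "will be associated with greater fear reduction in a self-directed exposure group relative to a control group". The SAP (Proposed Analyses) tests it with one ANOVA per outcome ("There will be 3 (group) x 2 (assessment) mixed measures analyses of variance (ANOVAs"). The outcomes are named in the same sentence: "with the DFS, and various DBAT measures (i.e., avoidance/escape, cardiac response, and SUDS verbal reports) as dependent variables". That makes four outcomes of equal standing: one questionnaire total and three measures from the simulated dental examination.

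The only quantitative design statement is in the Protocol under Participants. It targets 80% power "with two measurements and three groups at a medium effect size of .25" and arrives at a minimum total of 36. It ties the effect size to no outcome and gives no alpha. The SAP adds sensitivity analyses for baseline measurements without specifying them. Neither document has a primary outcome, an order of testing, an adjustment, or a statement of what pattern of results would support Hypothesis 1.

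**The concern.** Four tests bear on one hypothesis, and nothing says how to combine them. As the plan stands, a significant group-by-assessment interaction on any one outcome could be presented as support.

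The outcomes cover self-report, behaviour and physiology, so they may well disagree. If the DFS were null and heart rate significant, the reading of Hypothesis 1 would be chosen after the data were seen. That gap exists whatever alpha or correlation one assumes.

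Four may also be a minimum:
- The DFS has three subscales and is also taken by telephone at one week. The SAP does not say which two assessments enter the ANOVA.
- The DBAT has eight steps, and "A maximum-distress SUDS rating will be reported by the participants at the end of each step of the DBAT".
- The SAP does not say how the step-level SUDS and heart-rate data are summarised.

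**Working it through.** **Inputs from the documents.** Four outcomes, three groups and two assessments (SAP, Proposed Analyses); f = .25, power .80 and total N = 36 (Protocol, Participants).

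**Inputs assumed because the documents do not give them.** Alpha .05 per test; 12 per group; pre-post correlation .5 for the power figures; equal correlation between the four outcomes, varied from 0 to .9; and a rule that any one significant outcome counts. Three of the four outcomes come from the same DBAT session, so some positive correlation is plausible.

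**The plan's own figure.** With noncentrality λ = f² × N × m / (1 − ρ), m = 2 and ρ = .5, N = 36 gives λ = .0625 × 36 × 2 / .5 = 9.
- Time main effect (1 and 33 df): power .83. The smallest adequate N is 34, and 36 is the next multiple of three. The stated 36 is reproduced on this reading.
- Group-by-assessment interaction (2 and 33 df), which is what tests Hypothesis 1: power .73. N = 42 is needed for .80; 36 suffices only if ρ is about .6.

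The Protocol does not say which effect or ρ was used. This calculation is needed here only to price an alpha split.

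**False-positive rate, independent outcomes.**
- Any significant F: 1 − .95⁴ = .185.
- By symmetry, half of a single outcome's false positives have the pooled exposure groups better than control, so the rate is .05 / 2 = .025. For four outcomes it is 1 − .975⁴ = .096.

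**False-positive rate, correlated outcomes.** Simulation under the null: 100,000 trials per correlation, 3 × 12 participants, four equicorrelated normal change scores, a 2-df F test on each at .05.

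| Assumed correlation | At least one significant F | Same, with pooled exposure better than control | Same, with both exposure groups better than control |
|---|---|---|---|
| 0 | 18.6% | 9.6% | 6.5% |
| .3 | 17.7% | 9.2% | 6.2% |
| .5 | 16.0% | 8.3% | 5.6% |
| .7 | 13.7% | 7.1% | 4.7% |
| .9 | 9.8% | 5.1% | 3.4% |

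Repeat runs gave 13.3% to 13.7% for any significant F at .7, so the lower end is quoted as about 13%.

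**The opposite rule.** If all four outcomes had to be significant, the chance would be below 0.5% for correlations up to .7. The unstated success rule therefore moves the error rate from well below 5% to well above it.

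**Price of an equal alpha split.** At .05 / 4 = .0125 per test, the family-wise error is 1 − .9875⁴ = .049 if independent, and at most .05 under any correlation. With f = .25 and ρ = .5, omnibus interaction power at N = 36 falls from .73 to .51, and the N for .80 power rises from 42 to 60.

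**The case against.** A reader might infer that the trial has a 13-19% chance, instead of 5%, of falsely claiming fear reduction. The documents do not support that, for three reasons.

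1. **Wrong event.** The 13-19% counts any significant 2-df F. That includes control improving more than exposure, and the exposure groups merely differing from each other. Hypothesis 1 is directional, and a false finding in its direction is about 7-10%. The comparator is then about 2.5%, not 5%.
2. **No stated alpha.** That each test would be run at the full .05 is inferred from silence.
3. **Unstated conditions.** The figure also needs an any-one-counts rule and correlations no higher than .7. Outcomes from one DBAT session could correlate more strongly; at .9 the any-F rate is about 10%.

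All three stand, and they limit the figures to conditional ranges. They do not remove the omission. In the pooled direction the ratio to a single outcome is still 7.1 / 2.5 = 2.8 to 9.6 / 2.5 = 3.8.

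It can also be said that this is a small study whose lead questions are use and acceptability, with the hypotheses added to them. That is a fair description and argues against a harsher grade. But the SAP presents these ANOVAs as the assessment of treatment effectiveness, and the sample size was justified by power, so a stated decision rule is a reasonable expectation.

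Finally, no passage ranks the DFS above the behavioural measure. Choosing it is a judgement, and the sponsor could defend another choice if it is made in advance.

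**Conclusion.** The point holds as a conditional one. The omission is certain: four co-equal outcomes, with no primary, alpha, order, adjustment or success rule for Hypothesis 1.

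Its size depends on assumptions outside the documents. With alpha .05 and any one outcome counting, at least one false-positive F has a chance of about 13-19% for correlations of .7 to 0, and about 10% at .9. In the pooled hypothesised direction the chance is about 7-10% over the same 0 to .7 range, against about 2.5% for one outcome. If both exposure groups must beat control, it is about 5-6.5%.

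This should be corrected before data are seen. It does not invalidate the design.

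**What to change.** In the SAP:

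- State alpha .05 and name one primary outcome for Hypothesis 1 before data are seen. The DFS is the natural candidate: it measures dental fear directly and the SAP lists it first.
- Test it from baseline to week 2 by the exposure-versus-control contrast within the group-by-assessment interaction, not by the 2-df omnibus F. Under the Protocol's Procedure the exposure groups swap video perspective after week 1, so by week 2 both have been assigned both videos and appear to differ only in order. An omnibus F could be significant from that difference alone, which is not Hypothesis 1.
- Make the three DBAT measures secondary. Test them with Holm across the three only if the primary is significant; otherwise report them with confidence intervals as supportive.
- Define one summary each for DBAT cardiac response and DBAT SUDS, so that the secondary family really is three tests.

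The cost is a few sentences and one real restriction: a DBAT measure alone can no longer establish Hypothesis 1. The primary test keeps the whole alpha and so loses no power to multiplicity. The equal split shown above would instead take omnibus interaction power at N = 36 from .73 to .51, assuming f = .25 and a pre-post correlation of .5.
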